Specific Aim 2 (Research Aim): Conduct a Hybrid Type 2 pragmatic effectiveness-implementation trial of the adapted Telemedicine Blended model by assessing **RE-AIM** outcomes including: provider **Reach** into the patient population, **Effectiveness** at improving clinical outcomes, **Adoption** by providers and **Implementation** fidelity.

Hypothesis 1 (Reach): Compared to Veterans who receive the Referral model, a higher proportion of Veterans who receive the Telemedicine Blended model will have a MH encounter over a 6 month period.

Hypothesis 2 (Effectiveness): Compared to Veterans who receive the Referral model, Veterans who receive the Telemedicine Blended model will have better clinical outcomes at the 6 month follow-up.

Specific Aim 3 (Exploratory Aim): In this exploratory study, we will conduct qualitative interviews to identify up to 40 Veterans' perception of factors associated with implementation of VA-approved treatments for HCV, HIV, and mental health treatment among Veterans with documented health disparities of HCV and HIV (i.e., racial minority Veterans). Specifically, we aim to:

- a. Identify Veterans' experiences and preferences for HCV and/or HIV and mental health treatment.
- b. Identify barriers and facilitators to accessing HCV and/or HIV and mental health treatment.

Because there is a lack of scientific evidence documenting that the Blended model is effective in smaller CBOCs, PC-MHI does not currently mandate that it be delivered in these facilities. If the proposed study is successful, our clinical partners, [name] (MHS), [name] (PC-MHI) will use the results to justify implementation of the Telemedicine Blended model. Further, we can harness information gained in our exploratory aim to begin developing implementation strategies to better treat racial minority Veterans with HCV and/or HIV and depression, possibly through Care Management.

Study Design:

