We will employ the RE-AIM framework to assess Reach, Effectiveness, Adoption, Implementation, and Maintenance of the program. [name]-implementation, we will conduct interviews with key informants at each site to collect feedback which will help us to interpret outcomes at each site as well as to improve facilitation and implementation processes for future efforts.

Overall Study Design of Effectiveness Trial- The outcomes of the effectiveness trial will be based on the **RE-AIM** Framework (Reach, Effectiveness, Adoption, Implementation, Maintenance).⁴⁹⁻⁵² **Reach** represents the proportion of eligible or targeted patients who receive the EBP.⁴⁹ **Adoption** represents the proportion of staff who use the EBP.⁴⁹ **Implementation** represents the fidelity of the EBP as implemented in routine care.⁴⁹ **Effectiveness** represents the clinical impact (on patient outcomes) of the EBP as implemented in routine care settings.⁵¹ **Maintenance** represents the degree to which the implementation of the EBP is sustained.⁴⁹ The proposed effectiveness trial will focus on Adoption, Reach, Implementation Fidelity and Effectiveness. To have an impact on the health of the target population, an EBP must be adopted by providers, reach a large proportion of the targeted patient population, be implemented with high fidelity, effectively improve outcomes and be maintained after the research funds are withdrawn. Importantly, by measuring both *Reach* into the patient population and the *effectiveness* of those reached, we will be able to estimate the "population level impact" of PC-MHI.⁵³

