months prior to the first implementation period (for sites A and B) and continuing through the 6 month period following the implementation phase for sites E and F (see above diagram). We will exclude only those patients receiving specialty MH treatment in the 6 months prior to recruitment; those with a diagnosis of substance dependence; and those with a psychotic disorder diagnosis (schizophrenia, bipolar disorder, other psychotic disorders). Receipt of specialty MH care will be defined as having an encounter with a 500 series stopcode (except 534, which represents a PC-MHI encounter such as a telephone care manager encounter). The justification for this exclusion criterion is that patients enrolled in specialty MH care are already receiving a higher level of care than Telemedicine Blended and would not be expected to benefit clinically. The justification for excluding patients with substance dependence and a psychotic disorder diagnosis (schizophrenia, bipolar disorder, other psychotic disorders) is that currently there are no evidence based PC-MHI interventions for such patients. Finally, by focusing on all patients not already enrolled in specialty MH, it allows us to estimate the intervention's "population level impact" rather than its efficacy for a narrowly defined group of patients.⁵³

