Administrative Data: VA service utilization will be collected from the CDW, where all VA facilities upload and store encounter data, using methods we have employed previously.⁵⁴ Data will be collected on all patients at the study sites (hereafter referred to as the administrative sample) regardless of whether the patient was recruited and provided informed consent to participate in the primary data collection efforts associated with the trial. Encounter data will be collected for each patient for the 6 months following their first encounter in each 6-month observation period. Encounters to 500-599 stopcodes at CBOCs and VAMCs will be classified as MH. Encounters using the 534 stopcode (a stopcode used only for PC-MHI visits) will be classified as Telemedicine Blended. We will identify all patients (by scrambled social security number) with encounters to the study CBOCs and categorize them to the intervention or usual care group based on the date of their first encounter. We will also extract administrative data about MH diagnoses, age, gender, marital status, percent service connection and zipcode. MH diagnoses will be used to define diagnostic categories including: adjustment disorders, alcohol use disorders, anxiety disorders, attention deficit disorders, bipolar spectrum disorders, dementia, depressive disorders, drug use disorders, personality disorder, sleep disorders, stress reaction disorders, and other. The rurality of Veterans will be measured based on their zipcode using two different methods: 1) Rural Urban Commuting Area (RUCA) codes, and 2) VA definition. A zipcode to census tract crosswalk will be used. RUCAs are a census tract-based classification scheme that utilizes the standard Bureau of Census Urbanized Area and Urban Cluster definitions. RUCA also takes into account commuting patterns to Urbanized Areas, Urban Clusters, or smaller population centers to classify census tracts into 33 distinct categories, which typically are combined into 4 categories: 1) Urban - areas have Metropolitan cores and substantial commuting flow patterns to Urbanized Areas, 2) Large Rural Towns - have Micropolitan cores and substantial commuting patterns to Urban Clusters, 3) Small Rural Towns - have primary commuting flows to or within population centers of between 2,500 and 9,999 residents, and 4) Isolated Rural Towns - are less populated rural areas with no commuting flows to Urbanized Areas or Urban clusters.⁵⁵ VA's classification scheme defines census tracts that belong to Urbanized Areas as Urban and all others as Rural, except for those in counties with average population density of less than 7 residents per square mile, which are defined as Highly Rural.⁵⁵ The Real SSN Crosswalk file will be used to link primary data to the administrative data for participants enrolled in the effectiveness trial.

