
Dependent Variable for Adoption: Patients will be assigned to PCPs using the Patient Care Management Module from the Austin Automation Center which records every patient's PCP assignment start date and assignment end date. We have used this file successfully to measure provider adoption in a recent QUERI funded study (SDP 08-316). We will classify each Veteran in the administrative sample as having received Telemedicine Blended services if they had a 534 stopcode during their first encounter or a 534 stopcode encounter during the 6 month follow-up period. To measure provider adoption, we will categorize CBOC PCPs as adopters if they have at least one patient with the 534 stopcode encounter. In addition, we will document the percent of the PCP's patients that with a 534 stopcode encounter.

Data Analysis for Adoption - The percentage of PCPs adopting the intervention will be calculated. The adoption percentage will also be reported at the CBOC level.

Dependent Variable for Reach (Hypothesis 1): To measure Reach into the patient population, we will classify each Veteran in the administrative sample as having received MH services if they had a 500-599 series stopcode (including 534) during their first encounter or any encounter

during the 6 month follow-up period. Exploratory analysis will also examine *number* of MH encounters. We will also report the percentage of Veterans in the administrative sample who had a PC-MHI (534) stopcode during their first encounter or any encounter in the 6 month follow-up period in order to document the proportion randomized to the intervention who received Telemedicine Blended care.

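### Hypothesis 1 Reach is scored in every clinic patient, so Veterans already in specialty mental health care count as reached in either phase; this fits poorly with the plan's own definition of Reach and dilutes the effect

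*Combined protocol and SAP*

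**What the plan says.** Under Overall Study Design of Effectiveness Trial, Reach "represents the proportion of eligible or targeted patients who receive the EBP". Under Inclusion Criteria, Veterans with recent specialty mental health treatment are left out of the recruited sample because no clinical benefit is expected for them. The plan adds that "by focusing on all patients not already enrolled in specialty MH, it allows us to estimate the intervention's 'population level impact". The same section sets out how specialty care is recognised: "Receipt of specialty MH care will be defined as having an encounter with a 500 series stopcode", with 534 exempted.

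Hypothesis 1 uses a wider base. Administrative Data states: "Data will be collected on all patients at the study sites (hereafter referred to as the administrative sample". It goes on: "We will identify all patients (by scrambled social security number) with encounters to the study CBOCs". Follow-up runs for 6 months from the first encounter in each 6-month observation period. Dependent Variable for Reach (Hypothesis 1) then gives the scoring rule: "we will classify each Veteran in the administrative sample as having received MH services if they had a 500-599 series stopcode (including 534". No section applies the specialty-care exclusion, the diagnosis exclusions or a positive screen to this sample.

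Data Analysis for Reach (Hypothesis 1) adjusts for diagnostic category, demographics, service connection and rurality. Prior use of mental health care is not on the list.

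**The concern.** Specialty care is recognised by the same stopcode series that scores a Reach success. A Veteran who simply continues specialty visits is a success in the control phase and again in the intervention phase, and can enter once per observation period. Such records carry almost no information about whether the Blended model brings new Veterans into care, but they raise the baseline rate and pull the odds ratio towards 1.

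Two things are at stake. The tested quantity differs from the Reach that the plan defines. The plan also intends to join Reach with effectiveness to describe population-level impact, yet Reach comes from everyone seen at the clinic, while effectiveness comes from positive-screen Veterans outside specialty care.

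**Working it through.** **1. Is there a design figure to reproduce?** The plan gives no rates, sample size or power for Hypothesis 1. The one Reach figure in the documents is from the team's earlier implementation study (Preliminary Studies): 298/3,296 = 9.04%, stated as 9.0%, so it checks. Its denominator was primary care patients with depression who were not already in specialty care, which is the restriction that Hypothesis 1 lacks.

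**2. Unadjusted dilution.** All inputs are assumed: a mental health encounter in p0 = 5% (control) and p1 = 8% (intervention) of Veterans outside specialty care; 90% of specialty users in both phases; specialty share s = 10%, 20% or 30%.

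- Target-group odds ratio: (0.08/0.92)/(0.05/0.95) = 1.65.
- Clinic rate: 0.9s + (1−s)p. At s = 0.20: 0.18 + 0.04 = 0.220 against 0.18 + 0.064 = 0.244, odds ratio 1.14.
- Records multiple (how many times more records the all-patient test needs for the same z, compared with the restricted subset): [(1−s)d²/V] / [((1−s)d)²/V_all]. Here d = 0.03, V = 0.05×0.95 + 0.08×0.92 = 0.1211, and V_all is the same sum at the clinic rates. At s = 0.20: (0.8×0.0009/0.1211)/(0.024²/0.3561) = 0.005946/0.001618 = 3.7.

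**3. Best case for the planned adjustment.** Suppose diagnostic category identified specialty users perfectly.

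- Mantel-Haenszel odds ratio: [(1−s)p1(1−p0) + 0.09s] / [(1−s)p0(1−p1) + 0.09s]. At s = 0.20: (0.0608 + 0.018)/(0.0368 + 0.018) = 1.44.
- Records multiple: replace V_all by (1−s)V + 0.18s. At s = 0.20: 0.024²/0.1329 = 0.004335, and 0.005946/0.004335 = 1.4.

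| s | Clinic rates | OR, unadjusted | Records, unadjusted | OR, perfect adjustment | Records, perfect adjustment |
|---|---|---|---|---|---|
| 10% | 13.5% vs 16.2% | 1.24 | 2.3× | 1.54 | 1.2× |
| 20% | 22.0% vs 24.4% | 1.14 | 3.7× | 1.44 | 1.4× |
| 30% | 30.5% vs 32.6% | 1.10 | 5.1× | 1.35 | 1.6× |

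The planned model should fall between the two pairs of columns. A depression diagnosis, for example, does not tell a Veteran in specialty care from one who is not. Clustering is ignored throughout.

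**4. Sensitivity to the assumed rates.** With specialty users at 80% to 95% and s from 10% to 30%, the unadjusted multiple is 2.2 to 5.2 for 5% vs 8%, 1.5 to 2.9 for an assumed 9% vs 18%, and 1.3 to 2.2 for 9% vs 36%. The last pair is from the pre-post study of co-located care in the background section, in positive-screen patients and not specific to CBOCs. Every multiple exceeds 1, so in these cases the restriction gains precision although it discards records.

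**5. Which look-back?** The trial's exclusion rule exempts 534. The administrative sample is re-formed each period, so after a site's start date the look-back falls within intervention exposure. Assume no true change in access: 5% in non-users, 90% in continuing users. Let a fraction f of continuing users (share s) move from specialty codes to 534-only care.

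- Filter exempting 534: the control rate is 5%. The intervention rate is [(1−s)×0.05 + sf×0.9]/[(1−s) + sf].
- s = 0.20: f = 0.10 gives 0.058/0.82 = 7.1%, a false odds ratio of 1.45; f = 0.25 gives 0.085/0.85 = 10.0%, 2.11.
- s = 0.10: f = 0.10 gives 0.054/0.91 = 5.9%, 1.20; f = 0.25 gives 0.0675/0.925 = 7.3%, 1.50.
- Filter that also counts 534: continuing users drop out in both phases, 5% vs 5%, odds ratio 1.00. The whole-clinic odds ratio is also 1.00.

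**The case against.** The whole-clinic measure is a choice that can be defended. Hypothesis 1 names no eligible subset and asks only whether Veterans "will have a MH encounter over a 6 month period". The Reach section speaks of the patient population, and the Randomization section describes the model as a change to the whole clinic. Existing mental health staff are reallocated to deliver it, so specialty visits may fall, and only a whole-clinic figure shows the net effect on access. The exclusion of specialty users is written for recruitment. The percentage with a 534 encounter is reported separately and lies closer to receipt of the model itself.

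Most of this stands. A reader might infer that the plan flatly contradicts itself. The documents do not support that: a general definition of Reach and an explicit operational one fit badly together, and the operational one is stated openly. But none of these arguments makes continuing specialty users informative about new access, and the 534 percentage is descriptive and keeps the same denominator.

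The objection that diagnosis adjustment recovers part of the loss also stands, as step 3 shows. So does the objection to borrowing the trial's exclusion unchanged: step 5 shows that it can manufacture an effect.

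**Conclusion.** The point holds as a mismatch between the Reach that the plan defines and the Reach that it tests, with dilution towards no effect. The direction assumes that specialty users attend at about the same rate in both phases; if reallocation lowers specialty visits, the distortion goes beyond dilution. The size cannot be derived from the documents, which give neither the specialty share nor any Hypothesis 1 rate. The figures above are illustrations.

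A reader might infer that Hypothesis 1 is underpowered by a factor of two to five. The documents do not support that: the size of the administrative sample is not stated, the inputs are assumed, and those multiples leave out the planned adjustment. A reader might also infer that restricting the sample would make Reach and effectiveness describe one population. It would not, because Hypothesis 2 also requires a positive screen, the diagnosis exclusions and consent. The two would be better aligned, not matched.

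This is a minor point with a cheap remedy, and it leaves Hypothesis 2 untouched.

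**What to change.** Estimate Hypothesis 1 Reach in administrative-sample Veterans with no mental health encounter of any kind (500–599, including 534) in the 6 months before their first encounter in the period. Participant Recruitment and Consent already screens appointments on absence of any mental health encounter over that span. A look-back fixed before rollout is an alternative; it would need a stated rule for Veterans first seen later. Do not exempt 534, because eligibility would then depend on the intervention.

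Report the whole-clinic result alongside, to show any fall in specialty visits. If it stays primary, add mental health use in the prior 6 months as a covariate or stratum, with that look-back fixed before rollout.

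The cost is one filter on data already being extracted and a sentence or two in the analysis plan. The downsides are a smaller sample, low-need Veterans remaining in the denominator, and the residual difference from the Hypothesis 2 population, which the report should state when it discusses population-level impact.

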Integrating MH care into PC settings is a major priority of the OMHS.¹¹ The *Uniform Mental Health Services Handbook* mandates the blending of the two predominant, evidence-based models of integrated care (the Care Management model and the Co-Located model) at VAMCs, very large CBOCs, (>10,000 uniques) and large CBOCs (5,000-10,000 uniques).¹² Because there is no scientific evidence to support its implementation, the Blended model is not mandated at medium CBOCs (1,500-5,000 uniques) or small CBOCs (<1,500 uniques). Based on numerous experiences facilitating the deployment of integrated care models in CBOCs, our PC-MHI and VISN 16 Mental Health Product Line (MHPL) partners report that implementation of integrated care models is extremely challenging for CBOCs that lack a full range of MH staff (which also include many large CBOCs as well). These challenges are highlighted by findings of several preliminary studies described in the original grant application.

Briefly, we found that, while CBOCs are very important to the VHA healthcare system (half of primary care users receive care in CBOCs), the implementation of PC-MHI is lagging in these settings. While 6.2% of the PC encounters at VAMCs were PC-MHI encounters, only 2.9% of the PC encounters at CBOCs were PC-MHI encounters. Small and medium sized CBOCs had an even lower proportion of PC-MHI encounters. We have also shown that the co-located referral model, in which traditional "silo" MH services are physically co-located in a PC clinic, produces clinical outcomes that are inferior to outcomes of patients receiving enhanced referral to off-site mental health specialty care. Further, [name] (Co-I) and colleagues found that usual MH care (i.e., Co-Located Referral Model) results in sub-optimal outcomes for rural Veterans treated in small and medium CBOCs. However, a Care Management Model, developed by depression researchers based on the chronic care model,^{13,14} and specifically tailored by [name] for CBOCs that lack on-site psychiatrists and PhD psychologists, found significant improvements in adherence to medication, treatment response, and remission of depression for patients assigned to the care management condition as compared with those in usual care.^{15,16}

Preliminary Studies: [name], in collaboration with the Medical Directors of

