Patient Recruitment: We will initiate recruitment at all sites 3 months into the first 6-month study period (labeled as “Identify Model” in the diagram above), during the implementation planning for Sites A and B. We will complete recruitment 3 months before the data analysis period begins. Thus, Veteran follow up will extend into the first 3 months of the data analysis period for all sites. Since the duration of the implementation period may vary from site to site, we will consider a site’s first referral to the Telemedicine Blended Model (with a PC-MHI telemedicine stopcode) as the index date with all Veterans enrolled prior to that date designated as controls and all Veterans enrolled after that date designated as intervention participants.

Figure 1: Implementation Timeline

Grant months	Identify Model	Intervention						Data Analysis
		6 months	6 months	6 months	6 months	6 months	6 months	
Site A	Implementation Planning	Implementation PDSA	Step Down					
Site B			Step Down					
Site C			Step Down					
Site D			Step Down					
Site E			Step Down					
Site F			Step Down					

Inclusion Criteria: We will sample from the patient population who screen positive on routinely administered VA MH screens (e.g., depression, alcohol, PTSD) at the 6 CBOCs, beginning 6

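### Adoption counts any 534 encounter in any period, so primary care mental health integration (PC-MHI) care given before the new model started can label a provider as an adopter

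*Combined protocol and SAP*

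**What the plan says.** All references are to the combined protocol and SAP.

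- **Administrative Data** defines the sample broadly: "Data will be collected on all patients at the study sites", whether or not they consented, in each 6-month observation period. Patients are assigned to intervention or usual care by the date of their first encounter. On coding: "Encounters using the 534 stopcode (a stopcode used only for PC-MHI visits) will be classified as Telemedicine Blended".
- **Dependent Variable for Adoption**: "We will classify each Veteran in the administrative sample as having received Telemedicine Blended services" if a 534 code appears at the first encounter or in the 6-month follow-up. Then "we will categorize CBOC PCPs as adopters if they have at least one patient with the 534 stopcode encounter". A second measure follows ("In addition, we will document the percent of the PCP's patients that with a 534 stopcode encounter"), counted from the same code.
- **Data Analysis for Adoption** is purely descriptive: "The percentage of PCPs adopting the intervention will be calculated", also by CBOC. No test or comparison is planned.
- **Dependent Variable for Reach** also reports the percentage of the administrative sample with a 534 code. Its stated purpose is to show how many of those randomized to the intervention received the model.
- **Background**, on PC-MHI use found in preliminary work: "only 2.9% of the PC encounters at CBOCs were PC-MHI encounters", with a lower share at small and medium CBOCs.
- **Patient Recruitment** takes each site's "first referral to the Telemedicine Blended Model (with a PC-MHI telemedicine stopcode) as the index date". No code number is given there.

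**The concern.** The plan describes 534 as the code for PC-MHI visits generally, and the Inclusion Criteria give a telephone care manager encounter as an example. Such visits existed at CBOCs before this intervention. The plan also has a date on which the new model starts at each site, but the Adoption definition does not use it. Followed literally, the rule credits the intervention with care that came before it.

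Adoption is a named RE-AIM outcome of Specific Aim 2, in a hybrid trial that also tests an implementation strategy. If background use is appreciable, a high Adoption percentage could not be read as evidence that facilitation worked. The percent of each PCP's patients does not remove the difficulty, because it counts the same encounters.

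**Working it through.** **1. The plan's own figure.** The only adoption percentage in the documents comes from the earlier implementation study described in the Background: 58/84 = 69.0% of PCPs referred patients. This reproduces. No Adoption target is stated for the present trial.

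**2. Chance of being labelled an adopter from background use alone, assuming independence.** Let p be the background share of encounters coded 534 and n the number of encounters attributed to a PCP in the counting window. If p is read as a share of patients, n is panel size and the formula is the same.

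P(at least one) = 1 − (1 − p)^n

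**3. Does independence fit the documents?** The earlier study enrolled 298 patients across 84 PCPs, a mean of 298/84 = 3.55 per PCP. With patients spread at random (Poisson), 1 − exp(−3.55) = 97% of PCPs would have had at least one. The observed figure was 69.0%. Use therefore clusters by provider, and independence overstates the problem.

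**4. Allowing for clustering.** Under a negative binomial with dispersion k:

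P(at least one) = 1 − (1 + np/k)^(−k)

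Setting np = 3.55 and the result to 69.0% gives k = 0.612. For p = 2.9% and n = 300, np = 8.7, 1 + 8.7/0.612 = 15.2, 15.2^(−0.612) = 0.189, and the result is 81.1%.

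**5. Results.** The 2.9% is the Background's figure for all CBOCs. The lower rates and all values of n are assumptions.

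| p | n | np | Independent | Clustered |
|---|---|---|---|---|
| 2.9% | 100 | 2.9 | 94.7% | 65.7% |
| 2.9% | 300 | 8.7 | 99.99% | 81.1% |
| 0.5% | 300 | 1.5 | 77.8% | 53.1% |
| 0.5% | 500 | 2.5 | 91.8% | 63.0% |
| 0.1% | 500 | 0.5 | 39.4% | 30.6% |
| 0 | any | 0 | 0% | 0% |

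**6. What the figures mean.** Each is the share of PCPs who would meet the adopter definition with no intervention at all. It is not the amount by which reported Adoption would exceed true adoption, since some of the same PCPs would also use the new model after the index date. At 2.9% the clustered values lie close to or above the 69.0% that the earlier study reached with an actual programme.

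**The case against.** Much of the case on the other side stands.

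- **Background use may be small.** The 2.9% covers all CBOCs, including large ones. The study sites were to lack full-time on-site psychiatrists and psychologists or to have a major need for PC-MHI, and usual care is the Referral model. Use at the six sites could be near zero. This limits the size but does not repair the definition.
- **The wording may imply the intervention period.** Data Analysis for Adoption speaks of PCPs adopting the intervention, and the 534 percentage under Reach is meant for those randomized to it. For the Reach percentage that purpose is fairly clear, although the stated denominator is the whole administrative sample. For Adoption no date condition is written.
- **Other evidence is planned.** The percent of each PCP's patients, Adoption by CBOC, and chart-review fidelity for Veterans enrolled after the index date all help interpretation. None of them says which adopters qualified on pre-index care.
- **One patient is a defensible threshold.** The plan defines Adoption as the proportion of staff who use the practice, and any use fits that. The threshold matters here only because nothing limits when the encounter occurred.

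Three stronger readings are tempting and are not supported. A reader might infer that Adoption will saturate near 100%. That needs the all-CBOC rate together with independence, which the earlier study's own data contradict. A reader might also infer that only telemedicine-coded encounters are true intervention care. Telephone care management and face-to-face handoffs to an on-site social worker are part of the model or permitted adaptations of it, so that filter would miss genuine care. Finally, a reader might infer that the hypothesis tests are contaminated. Reach counts all 500-599 codes however 534 is labelled, and the Effectiveness outcome does not use the Adoption rule. The index date is defined by the first referral to the new model, not by any 534 visit.

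**Conclusion.** The concern holds as a defect of definition. As written, a PCP whose only 534 patient was seen before the model existed at that clinic is reported as an adopter, so Adoption can be inflated by background use. How far is unknown: nil with no prior use, and illustratively about 66% to 81% of PCPs at 2.9% (n of 100 to 300) and about 53% to 63% at 0.5% (n of 300 to 500). These figures rest on assumed volumes, on an all-CBOC rate that overstates small and medium clinics, and on a clustering parameter taken from a different programme that counted referrals and enrolments, so they are indicative only. The stakes are moderate: Adoption is a named Aim 2 outcome but is descriptive and untested. It should be corrected because the literal rule gives a wrong answer and the correction is easy.

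**What to change.** - Count a PCP as an adopter, and compute the already planned percent of each PCP's patients, only from 534 encounters dated on or after the CBOC's index date.
- Report both measures for the control period, from encounters dated before the index date, and present the after-versus-before difference. The date filter alone does not remove background PC-MHI that continues after the index date; the difference addresses it. Because the one-patient measure rises with the length of the window and control periods differ by wave, use windows of equal length, such as the 6-month observation periods already defined.
- Limit the 534 percentage under Reach to intervention-group patients, with the usual-care percentage beside it.
- Reconcile the PC-MHI telemedicine stopcode in Patient Recruitment with code 534 in Administrative Data and the Adoption definition. State whether they are the same code. Show any telemedicine-coded subset only as a supplement.

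The cost is a date filter and one extra tabulation on data already being extracted. The downside is that reported Adoption may be lower.
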